*ASSESSMENT OF VIDEO-CONFERENCE TECHNOLOGY
FOR POST-OPERATIVE FOLLOW UP IN A
UROGYNECOLOGIC POPULATION*

NCT04138810

[name]

July 16, 2018

Background

Telemedicine is being utilized at much higher rates than in the past by medical professionals across all specialties. Telemedicine includes traditional telephone calls, virtual office visits with video conferencing and even virtual rounding with robots. Its adoption into medical practice has been well received by both patients and medical staff and has become widespread throughout the United States. Many studies have documented that post-operative telephone calls made by nurses, advanced practice providers or the providers themselves decrease patient anxiety, decrease unnecessary emergency room visits and increase patient education and satisfaction with the surgery and the surgical team.¹⁻⁹ These telephone calls also provide an opportunity to triage patients who may warrant an earlier post-operative office visit for myriad of concerns.¹⁰⁻¹² With the ever expanding capabilities of technology and increased access and adoption of mobile technology we now have the opportunity to expand beyond the traditional phone call to interact with patients on a more interactive and personal level.¹³⁻¹⁵ The majority of the literature on hospital discharge follow up focuses on chronic disease conditions such as diabetes and congestive heart failure as these patients historically have multiple hospital re-admissions as their disease state progresses. The goals of close follow up of these patients were to ensure that patients were taking their medications and maximizing their health status as an outpatient to prevent costly inpatient management and admissions.^{4,16-20}

There is currently a paucity of literature surrounding the use of post-operative videoconferencing technology to supplement or replace the traditional post-operative office visit. Patients have routine post-operative office visits approximately thirty and ninety days after their surgical procedure. Often, the first post-operative visit consists mainly of reassurance and counseling, rarely does this visit have any major effect on clinical decision making. Replacement of the thirty day office visit with a virtual clinical encounter (VCE) can help alleviate travel and caretaker burden while still addressing post-operative needs and possibly increasing patient satisfaction.²¹ From the provider side, a VCE can help open up their office schedules to see more new patient consultations.²² An opportunity exists to improve the quality and efficiency of post-operative care and increase patient satisfaction by utilizing videoconferencing technology to conduct VCEs.

1. Czarnecki MLG, M. M.; Weisman, S. J. Advanced practice nurse-directed telephone management of acute pain following pediatric spinal fusion surgery. *J Spec Pediatr Nurs.* 2007;12(3):159-169.
2. Turner D. Can telephone follow-up improve post-discharge outcomes? *Br J Nurs.* 1996;5(22):1361-1365.
6. Yang CC, C. M. Effects of post- discharge telephone calls on the rate of emergency department visits in paediatric patients. *J Paediatr Child Health.* 2012;48(10):931-935.
7. Kleinpell RM. Improving telephone follow-up after ambulatory surgery. *J Perianesth Nurs.* 1997;12(5):336-340.
9. Gray RTS, M. K.; Badger, S. A.; Harvey, C. F. Post-operative telephone review is cost-effective and acceptable to patients. *Ulster Med J.* 2010;79(2):76-79.

This will be a prospective randomized control study comparing postoperative virtual clinical encounters versus traditional in-office postoperative visits in women undergoing pelvic reconstructive surgery. The postoperative experiences of both groups will be assessed via surveys.

Virtual Clinical Encounter Group:

- Receive video-conference call from office nurse 48-72 hours post discharge from hospital

- Receive video-conference call from fellow and/or attending physician approximately 30 days after surgery
- Complete telephone survey within 24 hours of 30-day videoconference visit
- Have in-office postoperative visit with fellow and/or attending physician approximately 90 days from surgery

Traditional Office Group:

- Receive telephone call from office nurse 48-72 hours post discharge from hospital
- Have in-office postoperative visit with fellow and/or attending physician approximately 30 days from surgery
- Complete telephone survey within 24 hours of 30-day office visit
- Have in-office postoperative visit with fellow and/or attending physician approximately 90 days from surgery

Study duration

In the division of urogynecology there are approximately 30-40 pelvic reconstructive surgical procedures a month (approximately 500 surgical cases across all clinical sites in the past year). We aim to start recruiting patients as soon as possible and estimate that we will need approximately 4 months to recruit the 50 patients for the study (25 in the virtual clinical encounter group and 25 in the traditional office group). Once the last patient is enrolled, data collection on the study would be completed after 3 months (a total of 7 months to complete data collection on the study). A subject's participation in the study will conclude 90-days after the date of their completed surgical procedure.

Accrual

Our primary outcome is patient satisfaction as determined by the validated PSQ-18. The minimum important difference has not been previously reported for the PSQ-18 but prior studies utilizing this questionnaire have shown that the standard deviation for total PSQ-18 scores range between 5 and 8 with a mean total score range between 67 and 72.24. With a non-inferiority margin of 5 points on the PSQ-18, a type I error rate of 0.05 and a power of 0.80, we estimated a sample size of 25 women per group.

Last year, the combined surgical volume of these cases at our clinical sites was approximately 500 subjects; thus, we anticipate we will be able to easily recruit the proposed sample size in 4 months. We plan to recruit women from 2 clinical sites in the University of Pennsylvania Health System: 1) Urogynecology at Hospital of University of Pennsylvania (HUP) and 2) Urogynecology at Pennsylvania Hospital (PAH). Physician investigators are present at all three sites, and will have opportunities to screen patients planning for surgery for pelvic organ prolapse for participation.

Key inclusion criteria

- Undergoing surgery for pelvic organ prolapse
- Age greater than 18
- Access to a smartphone
- Access to high speed internet access (via 4G or 3G on their smartphone or high speed Wi-Fi)
- Signed up for MyPennMedicine web portal
- Ability to download MyChart mobile application
- Pennsylvania Hospital Subject: NJ or PA resident, HUP & Presbyterian Hospital Subject: PA resident

Key exclusion criteria

[figure not shown]
- Pregnancy
- Inability to read, speak or understand English
- Isolated midurethral sling procedure
- Extraperitoneal vaginal colpopexy with Uphold mesh

Procedures

RECRUITMENT AND PREOPERATIVE PERIOD: We plan to recruit women from 2 clinical sites associated with the University of Pennsylvania Health System: 1) Urogynecology at Hospital of University of Pennsylvania (HUP) and 2) Urogynecology at Pennsylvania Hospital (PAH). All patients will fill out the Patient Technical Qualifying Checklist to verify that they meet the technical requirements needed for participation in the study. If the patient is not currently enrolled in My Penn Medicine or does not currently have the MyChart mobile application downloaded onto their smartphone, then the trained office staff at the clinical sites will assist the patient in obtaining these requirements for participation. Physician investigators, who are present at all sites, will screen patients planning for

surgery for pelvic organ prolapse for participation. Following confirmation of eligibility, the physicians will obtain informed consent prior to surgery at the planned preoperative visit. The combined annual surgical volume at our two clinical sites (four surgeons) is approximately 500 subjects; thus, we anticipate we will be able to easily recruit the proposed sample size in seven months.

ENROLLMENT AND PERIOPERATIVE PERIOD: After informed consent has been signed, the patients will be randomized to either postoperative virtual clinical encounters (VCE) via videoconference technology or traditional in-office post-operative visits using sealed, opaque, sequentially numbered envelopes following a blocked randomization schedule. The patient will undergo their planned surgery, if there are any surgical complications from surgery that warrant in-office visits, those patients randomized to virtual clinical encounters will be removed from the study and undergo the current standard of care with in-office postoperative visits. If there are no complications from surgery then the following follow up encounters will occur for the two groups.

POSTOPERATIVE PERIOD: As per standard of care, all subjects will be scheduled for a nursing clinical encounter 48-72 hours following discharge from the hospital from their surgery. The VCE group will conduct their encounter via the videoconference section of the MyChart mobile applications. The traditional follow up group will receive a telephone call from the office nurse as is current standard of care. Both of these encounters will be conducted according to a standard script which reviews the following key aspects of postoperative care: bowel functions, voiding functions, presence of vaginal bleeding, pain control, diet status, ambulatory status and any additional concerns. Standard postoperative instructions and precautions are reviewed as well. At the end of this nursing encounter, the office nurse will schedule the patient for a 30-day postoperative visit. This will either be a VCE or an in-office visit, depending on the subject's randomization. These encounters are documented in the electronic

medical system. If at any time the patient who is randomized to VCEs no longer desires to be in the VCE group, an in-office appointment will be scheduled for them by the office nurse.

On the scheduled day of the 30-day postoperative visit the VCE group will conduct their visit via the videoconference section of the MyChart mobile applications with the clinical fellow and/or their surgeon. The traditional group will have their in-office visit with the clinical fellow and/or their surgeon. Both encounters will be conducted according to a standardized script. Subjects will all be offered a physical exam if desired. If a subject in the VCE group desires a pelvic exam, then they will be offered to come into the clinic on the next following business day. These encounters are documented in the electronic medical system.

Demographic information will be collected from the patient's medical record (age, ethnicity, level of education, medical comorbidities, and duration of hospitalization). Data regarding the patient's surgical intervention (procedure type, surgical complications, operative time) will be collected from the operative record. Within 24 hours of completion of the 30-day visit, the subject will receive a telephone call from the research staff and a phone survey of the study questionnaires will be conducted.

All patients will be scheduled for an in-office visit for their 90-day postoperative visit. On the scheduled day of the 90-day postoperative visit the visit will be conducted by the clinical fellow and/or their surgeon. This will be conducted according to a standardized script. All subjects will receive a physical exam. This encounter is documented in the electronic medical system.

Analysis Plan

All analyses will be conducted using an intent-to-treat principle. Data between groups will be analyzed using two-sample t-tests, Wilcoxon rank-sum tests, Pearson chi-square and Fisher's exact tests, as appropriate. Non-inferiority will be determined by the PSQ-18 after the 30-day postoperative visit with a non-inferiority margin of 5 points.

Consent

Informed consent will be obtained by the investigator in the clinical office during the subject's preoperative office visit. The patient may choose to withdraw from the study at any time. Investigators will emphasize that participation (or lack of participation) in the study: 1) will not influence their evaluation, care, or treatment 2) is completely voluntary 3) does not involve any financial compensation 4) may be terminated at any time. Layman terms will be used by those obtaining the consent. The consent will be written at a 6th grade reading level. All questions will be answered to the patient's satisfaction and understanding before informed consent is obtained.

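### The protocol disagrees with itself on whether there are two or three recruiting sites, and it does not say whether randomisation or analysis takes account of site

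*Combined protocol and SAP*

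**What the plan says.** On sites, Accrual states: "We plan to recruit women from 2 clinical sites in the University of Pennsylvania Health System", and names HUP and PAH. Procedures (recruitment and preoperative period) repeats that list and adds: "The combined annual surgical volume at our two clinical sites (four surgeons) is approximately 500 subjects". Accrual also says: "Physician investigators are present at all three sites". Presbyterian Hospital appears only in the residence rule under Key inclusion criteria: "Pennsylvania Hospital Subject: NJ or PA resident, HUP & Presbyterian Hospital Subject: PA resident". Under that rule a New Jersey resident can enter only at PAH.

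On randomisation, Procedures (enrolment and perioperative period) says that patients are allocated after consent "using sealed, opaque, sequentially numbered envelopes following a blocked randomization schedule". It gives no block size, strata, number of envelope sets or place where they are kept.

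On analysis, the Analysis Plan names standard two-group parametric, rank, chi-square and exact tests and a PSQ-18 margin of 5 points. It mentions no site term or other covariate. The planned size is 25 women per arm.

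**The concern.** There are two linked problems.

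The first is a contradiction in eligibility. Someone screening a Presbyterian patient cannot tell from the protocol whether she may be enrolled, and someone preparing envelopes cannot tell how many offices to supply.

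The second is an omission. Site is a plausible prognostic factor here. The residence rule gives the hospitals different catchments, satisfaction is scored just after the 30-day visit, and the efficiency outcome includes waiting-room, exam-room and provider time, which may depend on the office. Blocking alone balances the total numbers per arm, not the numbers per arm within each site. With 50 patients and no site term in the analysis, a chance imbalance would pass into the estimated difference. At stake is some precision in a small non-inferiority comparison.

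**Working it through.** **Site count, side by side**

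| Section | Sites |
|---|---|
| Accrual, recruitment sentence | 2 (HUP, PAH) |
| Accrual, next sentence | 3, not named |
| Key inclusion criteria, residence rule | 3 named (PAH, HUP, Presbyterian) |
| Procedures, recruitment sentence | 2 (HUP, PAH) |
| Procedures, surgical volume | 2 |

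Three statements say two sites. One says three, and one criterion provides for a third hospital.

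**The plan's own sample size.** Accrual gives "With a non-inferiority margin of 5 points on the PSQ-18, a type I error rate of 0.05 and a power of 0.80" and says that the "standard deviation for total PSQ-18 scores range between 5 and 8". Assume SD 7 (inside that range), one-sided alpha 0.05 (sidedness is not stated) and a true difference of 0:

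n = 2 × (1.645 + 0.842)² × 7² / 5² ≈ 24.2, so 25 per arm.

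Exact t-test power at 25 per arm is 0.801, so the stated figure reproduces. The standard error of the arm difference is 7 × √(2/25) = 1.98 points.

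**Chance imbalance if the schedule is unstratified.** The documents give no site split, so assume two sites with M of the 50 patients at the smaller one. The number X of those patients in one arm of 25 is hypergeometric, and the difference in site share is (2X − M)/25.

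| M | P(difference ≥ 20 points) | SD of share difference |
|---|---|---|
| 10 | 0.074 | 0.114 |
| 15 | 0.217 | 0.131 |
| 20 | 0.148 | 0.140 |
| 24 | 0.156 | 0.143 |
| 25 | 0.258 | 0.143 |

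The probabilities do not rise steadily because X is a whole number. With M even, the first attainable value at or above 20 points is 6/25 = 24 points; with M odd it is 5/25 = 20. The SD column is the steadier summary. Simulating one common sequence in blocks of 4 or 6 (sizes assumed) with an expected site share of 30% or 50% gives 0.15 to 0.18. With separate blocked sequences for two sites, none of 6,000 runs per scenario reached even 10 points, and the root mean square difference fell to about 0.03.

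**Effect on the PSQ-18 difference.** Shift = imbalance × between-site difference. The documents give no between-site difference, so 2, 3 and 5 points are assumed.

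- 0.20 × 2 = 0.4 point, or 8% of the margin
- 0.20 × 3 = 0.6 point, or 12%
- 0.20 × 5 = 1.0 point, or 20%, which is 1.0/1.98 = 0.51 of a standard error

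**Error rates.** Between-site variation is already part of the total SD. In simulation with a 25/25 site split, total SD 7 and a 5-point site difference, an unstratified trial with the plain t-test had type I error of about 0.05 at the margin. What stratification and adjustment recover is precision. With equal sites the within-site variance is 49 − d²/4:

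- d = 2: 49 − 1 = 48, SD 6.93; simulated power about 0.81 against 0.80
- d = 5: 49 − 6.25 = 42.75, SD 6.54; simulated power about 0.84 against 0.80

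**The case against.** The strongest reply is that nothing here threatens validity, and that stands. Randomisation without site strata is valid. An imbalance is equally likely to favour either arm, and only half of such imbalances would favour the video arm. The residence rule is applied before allocation, so it shapes who enters the trial and cannot by itself make the arms differ. All sites belong to one division with four surgeons and scripted encounters, so the site effect may be small. The 5-point value is about the spread of mean scores across separate earlier studies, not between offices of one service. It is best treated as an upper value.

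A reader might also infer that the trial uses one unstratified envelope sequence. The documents do not say so. They are silent on strata and on the number of sets, and separate sets per site are neither stated nor excluded. Nor does it follow that a single numbered sequence could not be opened in order from several offices: a centrally held set, opened on request, would manage this, and the protocol does not place the envelopes in the offices.

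What the reply leaves untouched is the contradictory site list, the missing allocation details and the absence of any site term.

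**Conclusion.** The contradiction on sites is plain in the text and needs reconciling, whatever one thinks of the statistics. On allocation and analysis, the supportable finding is that handling of site is unspecified.

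If the schedule is unstratified, a site-share difference of 20 points or more has a chance of about 7% to 26% across splits from 10/40 to 25/25. The top figure holds only at an exactly even split. Such an imbalance moves the PSQ-18 difference by 0.4 to 1.0 point for site differences of 2 to 5 points. The site split, the site effect and SD 7 are all assumptions. The consequence is lost precision, worth roughly 1 to 4 percentage points of power in the cases simulated. The documents do not support reading it as bias or as a higher false non-inferiority rate. Severity: minor.

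**What to change.** Make the site list identical in Accrual, the residence criterion and Procedures, so that Presbyterian is either a recruiting site throughout or appears nowhere. State the block size or sizes and who holds the envelopes. Prepare a separate blocked schedule and numbered envelope set for each recruiting site. Include site as a factor in the PSQ-18 non-inferiority comparison and in the efficiency comparison.

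The planned 50 patients do not change. The cost is one degree of freedom for two sites or two for three, and possibly an incomplete block at each site. In the two-site simulations the arm totals never differed by more than 2 patients with blocks of 4, or 4 with blocks of 6. If the sites turn out to be alike, the gain will be small.

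### After randomisation, virtual-visit patients with qualifying surgical complications leave the study; no matching rule is stated for the office arm, and the literal wording conflicts with the intent-to-treat plan

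*Combined protocol and SAP*

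**What the plan says.** **Order of events.** Under Procedures (Recruitment and Preoperative Period), "the physicians will obtain informed consent prior to surgery at the planned preoperative visit". The Enrollment and Perioperative Period paragraph randomises once consent is signed and only then describes the operation. A surgical complication is therefore a post-randomisation event.

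**Removal rule.** The same paragraph says that if surgical complications warrant office visits, "those patients randomized to virtual clinical encounters will be removed from the study and undergo the current standard of care with in-office postoperative visits". It names the virtual clinical encounter (VCE) arm only.

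**Office arm.** The next sentence reads: "If there are no complications from surgery then the following follow up encounters will occur for the two groups". It does not say what happens to an office patient with a complication, and it removes nobody.

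**Analysis.** The Analysis Plan states: "All analyses will be conducted using an intent-to-treat principle". It gives no exception, no modified population and no rule for the data of removed patients.

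**The concern.** A patient who has left the study cannot, on the plain meaning of the words, also be followed and analysed in the arm to which she was randomised. The plan gives both instructions and does not reconcile them, so the analysis set for the primary PSQ-18 comparison is unsettled for these patients.

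If office patients with the same complications stay in, the VCE arm is selected on something that happened after randomisation and the office arm is not. The satisfaction comparison can then move in either direction. The secondary outcomes are exposed too: postoperative complications is one of them, and emergency visits, readmissions and unscheduled office visits may well be related to complications. Patients prone to such events would drop out of one arm only.

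**Working it through.** **Inputs from the documents (Accrual, Analysis Plan).** Margin 5 points, type I error 0.05 (sidedness not stated), power 0.80, SD between 5 and 8 (value used not stated), 25 per arm.

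**Reproducing the plan's figure.** n per arm = 2 × SD² × (1.645 + 0.842)² / 5², one-sided 0.05, true difference 0:
- SD 5: 12.4, rounded up to 13
- SD 7: 24.2, rounded up to 25
- SD 8: 31.7, rounded up to 32

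The stated 25 is matched at SD 7, which I use below. SD 7 and the one-sided level are my inference. The sample size is not in dispute here.

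**Assumptions not in the documents.** A share c of 5%, 10% or 20% qualifies for removal. Complicated patients score D points lower than others. Higher scores mean greater satisfaction.

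**Chance that the rule is used.** Expected removals among 25 VCE patients are 25 × c = 1.25, 2.5 and 5. The chance of at least one is 1 − (1 − c)^25 = 0.72, 0.93 and 0.996.

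**Shift if only VCE patients are removed.** Shift = c × D. With D = 5 this is 0.25, 0.5 and 1.0 point of the 5-point margin.

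**False non-inferiority.** Let the true VCE deficit equal the margin. Approximately, P = Φ(c × D / SE − 1.645), with SE = 7 × √(1/25 + 1/(25(1 − c))). For c = 20% and D = 5, SE = 7 × √(0.04 + 0.05) = 2.1, and Φ(1.0/2.1 − 1.645) = Φ(−1.169) = 0.12.

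Simulation of the pooled t lower bound (100,000 trials per cell, SD 7) gives:

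| Complicated patients' score | c = 5% | 10% | 20% |
|---|---|---|---|
| Same | 0.05 | 0.05 | 0.05 |
| 5 lower | 0.065 | 0.08 | 0.115 |
| 10 lower | 0.08 | 0.115 | 0.21 |
| 5 higher | 0.04 | 0.03 | 0.017 |
| 0, 5 or 10 lower, removed from both arms | 0.05 | 0.05 | 0.05 |

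Entries are approximate. With a 5-point lower score, the figures are 0.070, 0.094 and 0.152 at SD 5, and 0.063, 0.076 and 0.106 at SD 8.

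**Precision.** Losing 5 of 25 VCE patients lowers power from 0.80 to 0.76 (noncentral t, SD 7). The loss is small; selection is the larger issue.

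**Checking the remedy (all patients kept, analysed as randomised, SD 7).**
- If the whole VCE arm has a 5-point deficit, false non-inferiority is about 0.05 whatever D is.
- If the deficit exists only in those who actually receive VCE, crossover shrinks it to 5 × (1 − c) = 4.75, 4.5 and 4.0 points. P(non-inferior) is then about 0.06, 0.08 and 0.12.
- If complicated patients score 10 points lower, the SD becomes √(49 + 100 × c × (1 − c)) = 7.33, 7.62 and 8.06. Power at a true difference of 0 falls from 0.80 to about 0.77, 0.74 and 0.70.

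**The case against.** **Removal may mean only leaving the video pathway.** The sentence goes on to describe office follow-up. On that reading these patients are still followed and analysed as randomised, and the two rules are compatible. This is possible, so a reader who infers that the rules can never both be followed goes too far. It is the less literal reading, though. The Postoperative Period paragraph deals with a VCE patient who changes her mind by booking an office appointment, with no mention of leaving the study. Nothing in the plan states the softer meaning.

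**The removal may cover both arms.** The sentence about uncomplicated surgery can be read to mean that only uncomplicated patients in either arm continue. There would then be no one-arm selection, and the error rate stays near 0.05 in the illustration. This stands as a possibility. It is not stated, and it would still conflict with intent-to-treat.

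**The bias is not demonstrated.** This is correct. A reader might infer that the rule favours VCE. The documents give no complication rate and no score difference, and the effect reverses if complicated patients are more satisfied.

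**The 90-day participation statement.** A reader might see a further contradiction in "A subject's participation in the study will conclude 90-days after the date of their completed surgical procedure". That is a general statement of duration, and the Consent section allows withdrawal at any time. It adds nothing to the point.

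**As-randomised analysis can itself favour non-inferiority.** For the effect of receiving VCE this is right. With no score difference the present wording gives about 0.05 where the as-randomised analysis gives 0.06 to 0.12. This is a cost to declare. It does not justify leaving the analysis set unsettled.

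**Conclusion.** The point holds, and the plan is wrong as written. Read literally, it takes patients out of one arm on a post-randomisation event while promising intent-to-treat throughout, and nothing reconciles the two. It should be corrected before enrolment, because outcomes not collected on removed patients may not be recoverable.

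The seriousness rests on the contradiction, not on a proven bias. The illustrated false non-inferiority rates run from 0.017 to 0.21 at SD 7, depending wholly on assumed removal rates, assumed score differences and the assumption that office patients are kept. The documents do not support a claim that the result would be biased towards VCE, or that the loss of numbers alone would matter much.

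**What to change.** Reconcile the Enrollment and Perioperative Period paragraph with the Analysis Plan, leaving clinical care as it is:

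1. Replace the removal wording with a statement that these patients have the office follow-up already described there but stay in the study.
2. Collect the PSQ-18 and the 30- and 90-day outcomes on every randomised patient.
3. Analyse all of them in the arm assigned.
4. Report by arm how many had a qualifying complication.

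**Cost.** A wording change, and outcome collection on an expected 1.25 to 5 VCE patients under the assumed rates. No visits are added. The survey is already by telephone ("Within 24 hours of completion of the 30-day visit, the subject will receive a telephone call from the research staff"), and the complication data are already planned: "Data regarding the patient's surgical intervention (procedure type, surgical complications, operative time) will be collected from the operative record".

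**Downsides to state in the plan.** The as-randomised analysis estimates the effect of assigning VCE, and crossover dilutes a deficit confined to those who receive it. If complicated patients score much lower, the added variance reduces power. Both are sized in the working.

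**Optional.** The sponsor may add a supportive per-protocol analysis that applies one complication criterion to both arms. Resolving the contradiction does not require it.

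### VCE women whose surgical complications warrant office visits are removed after randomisation, with no matching rule for the office arm, so the promised intent-to-treat primary analysis cannot be done as written

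*Combined protocol and SAP*

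**What the plan says.** Consent is obtained at the preoperative visit and randomisation follows consent, so allocation precedes surgery (Procedures, Recruitment and Preoperative Period, and Enrollment and Perioperative Period). The latter then sets a rule that depends on what happens in surgery. Its trigger is: "if there are any surgical complications from surgery that warrant in-office visits". The consequence, stated for one arm, is that "those patients randomized to virtual clinical encounters will be removed from the study and undergo the current standard of care". The next sentence reads: "If there are no complications from surgery then the following follow up encounters will occur for the two groups".

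A VCE woman who changes her mind is handled differently. If she "no longer desires to be in the VCE group, an in-office appointment will be scheduled for them by the office nurse"; removal is not mentioned (Procedures, Postoperative Period).

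The Analysis Plan states: "All analyses will be conducted using an intent-to-treat principle". For the primary outcome: "Non-inferiority will be determined by the PSQ-18 after the 30-day postoperative visit with a non-inferiority margin of 5 points". The survey is tied to that visit: "Within 24 hours of completion of the 30-day visit, the subject will receive a telephone call from the research staff". The Design section ties the VCE arm's survey specifically to the videoconference visit. Some surgical data come from another source: "procedure type, surgical complications, operative time) will be collected from the operative record". No method for missing data is given.

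**The concern.** The removal rule acts on an event after randomisation and names one arm only. If office-arm women with the same complications stay in, the primary comparison becomes VCE women without such complications against all office women, and randomisation no longer protects it. The promise of intent-to-treat and the removal rule cannot both be followed for the PSQ-18, because removal comes before the PSQ-18 is measured.

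The secondary outcomes are exposed too. Emergency room visits, readmissions, unscheduled visits and postoperative complications are what one would expect to differ in women with surgical complications, and these would be compared between unlike groups. What makes a complication warrant an office visit is not defined, so removal is a matter of judgement by staff who know the arm. With 25 women per arm, each removal takes 4% of the VCE arm.

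**Working it through.** **Inputs from the plan (Accrual).** Margin 5 points; type I error 0.05, sidedness not stated; power 0.80; SD between 5 and 8, value used not stated; 25 per group.

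**The plan's own figure.** With SD 7 and one-sided 0.05, n = 2 × 7² × (1.645 + 0.842)² / 5² = 24.2, rounded up to 25 per group. The noncentral-t power at 25 v 25 is 0.801. One-sided 0.025 with an SD of about 6.3 also gives 25. The sample size is not in dispute; SD 7 and one-sided 0.05 are used below.

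**Shift caused by removal.** Assume that k of 25 women in each arm meet the trigger and score d points lower, and that those in the office arm stay in. The office mean then falls by kd/25. The VCE mean does not, because its k women are gone. The difference (VCE minus office) shifts by kd/25 towards VCE. Both k and d are assumptions.

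**False non-inferiority.** Let VCE be truly 5 points worse. The noncentrality is (kd/25)/SE, with SE = 7 × √(1/(25−k) + 1/25).
- k = 1, d = 3: shift 0.12 (2% of the margin), SE 2.000, noncentrality 0.060, probability 0.056.
- k = 2, d = 5: shift 0.40 (8%), SE 2.022, noncentrality 0.198, probability 0.074.
- k = 5, d = 7, an extreme case: shift 1.40 (28%), SE 2.100, noncentrality 0.667, probability 0.161.

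The reference value is 0.050. For the first two cases the probabilities are 0.059 and 0.085 at SD 5, and 0.056 and 0.070 at SD 8.

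**Opposite sign.** If these women score d points higher, for instance because of extra contact, the three probabilities are 0.044, 0.033 and 0.011. Power at no true difference falls from 0.801 to 0.776, 0.724 and 0.517. With d = 0 there is no shift.

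**What retention does and does not repair.** If the k women switch to office visits and stay in, the comparison of assigned follow-up policies is free of this shift. The effect of video itself is diluted. If switched women have no video effect, a 5-point deficit on video becomes 5 × (25 − k)/25 = 5 − 0.2k. For k = 1, 2 and 5 it is declared non-inferior with probability 0.061, 0.074 and 0.126. Dilution of 0.2k equals the removal shift of kd/25 at d = 5. Below that gap, removal distorts the video effect less than retention does.

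**Per-protocol power.** Excluding k trigger women from both arms, with SE = 7 × √(2/(25−k)) and no true difference:
- k = 1: SE 2.021, power 0.786.
- k = 2: SE 2.064, power 0.770.
- k = 5: SE 2.214, power 0.717.

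**The case against.** The strongest reply is that the asymmetry is not stated. The plan never says that complicated office-arm women stay in, and the sentence after the removal rule, read literally, makes the planned encounters in both groups conditional on no complications. If such women left both arms, the one-sided shift above would largely disappear. This stands as a limit on certainty. However, the removal rule names only VCE women, so their staying in is the natural inference, and even the symmetric reading is a departure from intent-to-treat.

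A second reply is that removal may mean only a change to office care. The rule gives both instructions, removal and standard care, and the handling of women who change their mind shows that office care does not need removal. If a switch was meant, the remedy is a wording change.

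A reader might also infer that every outcome is lost for removed women. The documents do not support that. Surgical complications come from the operative record, clinical encounters are documented electronically, and removed women still receive office care, so some secondary outcomes may be recoverable. The PSQ-18 is a telephone survey and is not. The plan does not forbid surveying removed women, but it does not provide for it either.

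Finally, the effect may be small: 2% and 8% of the margin in the two moderate cases. That is fair, and it limits how strongly the point can be put.

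**Conclusion.** The plan is wrong as written on this point. A removal rule acting after randomisation, stated for one arm, contradicts the promise of intent-to-treat for the primary outcome. That conclusion needs no assumed numbers.

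The bias does rest on assumptions: that complicated office-arm women stay in, and that they differ in satisfaction. A reader might infer that the rule makes non-inferiority easier to declare. That holds only if women with complications are less satisfied, which the documents do not say; if they are more satisfied, the rule works against VCE. The probability of 0.161 should not be read as an expected result, since it needs 5 of 25 women affected with a 7-point gap. In the two moderate cases it is 0.056 and 0.074 against 0.050.

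Nor does intent-to-treat alone control the error rate for the effect of video. It answers the policy question, which the protocol has not yet named as its target. The change should be made because the contradiction is clear and the repair is cheap, not because a large bias has been shown.

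**What to change.** 1. In Enrollment and Perioperative Period, replace removal with a switch to office visits while remaining in the study. In "If there are no complications from surgery then the following follow up encounters will occur for the two groups", delete the opening condition.
2. For every randomised woman, make the PSQ-18 call after whichever 30-day visit takes place, collect all 30- and 90-day outcomes, and analyse as randomised. Align the Design section, which ties the VCE survey to the videoconference visit, and the Postoperative Period text, which fixes the type of 30-day visit by allocation.
3. State that the primary comparison is between assigned policies: VCE with office visits when needed, against office visits.
4. Add a supportive per-protocol analysis that excludes, from both arms alike, women who meet a complication list written before enrolment. Rating by someone not told the arm is a useful option. Report how many VCE women switched by preference, and note that this analysis does not remove the dilution from those switches.

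**Cost.** A few sentences, a short complication list, and one extra phone survey per affected woman. No extra patients are needed, and no extra visits, since women who would have been removed already receive office visits. The per-protocol analysis has somewhat lower power: 0.786 to 0.717 with 1 to 5 women excluded per arm, against 0.801 (SD 7).
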